7.3. Removal of Subjects from Study Therapy

A subject may be removed from the study therapy for a variety of reasons, including:

- Unacceptable adverse event
- Subject unwilling or refusal to continue with the protocol defined study visits and/or consent withdrawal for study participation
- Change in compliance with an inclusion/exclusion criteria
- General or specific changes in the subject's condition that render the subject unacceptable for further treatment in this study in the judgement of the investigator.

If a subject is to be withdrawn from the study, the Aclaris Therapeutics, Inc. CRA or designee must be informed within 24 hours of the decision to remove the subject from the study.

Aclaris Therapeutics, Inc.

Protocol Number: A-101-WART-303

Protocol: Version 3: 14 February 2019

The study may be discontinued at the discretion of Aclaris Therapeutics, Inc. Some examples of reasons for discontinuation are the occurrence of the following:

- Increased frequency, severity or duration of known AEs
- Medical, regulatory or ethical reasons affecting the continued performance of the study
- Difficulties in the recruitment of subjects

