⁴ Investigational site staff will be required to make a phone contact with the subject on Day 15, Day 43, Day 102 and Day 144 to assess for any safety issues and possible new concomitant medications the subject may have started taking. In addition, subjects are to ask if they have had any new warts develop since the last in office visit.

⁵ Subjects over the age of 18 are to apply the A-101 study medication on the following days: Day 1, Day 4, Day 8, Day 11, Day 15, Day 18, Day 22, Day 25, Day 29, Day 32, Day 36, Day 39, Day 43, Day 46, Day 50 and Day 53. A window of +1 day is allowed. Subject between the ages of 1-17 will have their A-101 study medication applied by a parent or guardian. Parents/legal guardians of children must ensure that the child does not put the treated area in their mouth, or eyes, until completely dry after the application. If the treated area is not completely dry 10 minutes after the application, the area should be blotted dry.

⁶ A-101 will only be dispensed to subjects who have not cleared all their warts, or who have developed new warts, and will be starting a new 8-week treatment cycle.

Table 3 Safety Observation Assessments for Subjects that are Clear at Visit 1 and Remain Clear

Visit	V1	V2	V3	V4	EOS
Treatment Day	Day 1	Week 6 (Day 42)	Week 12 (Day 84)	Week 18 (Day 126)	Week 26 (Day 182)
Window		+7 Days	+ 7 Days	+ 7 Days	+ 2 Days
In Office Visit	▲ ¹				▲

Aclaris Therapeutics, Inc.

Protocol Number: A-101-WART-303

Protocol: Version 3: 14 February 2019

Visit	V1	V2	V3	V4	EOS
Phone Call		▲ ²	▲ ²	▲ ²	
Informed Consent	▲				
Inclusion Criteria/Exclusion Criteria	▲				
Concomitant therapies		▲	▲	▲	▲
Adverse Events	▲	▲	▲	▲	▲

¹Visit 1 of A-101-WART 303 may occur on the same day as Visit 13 of A-101-WART 301 or A-101-WART 302.

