#### 3.2 Treatment Groups and Data Presentation

This is an open-label study with only one treatment arm. Subjects who enter the study with a common wart receive study medication immediately. Subjects who enter the study with no common warts do not receive study medication at the start and will not be treated at all if they do not develop any common warts throughout the course of the study. In order to be eligible for this study, subjects must have completed protocol treatment on either the A-101-WART-301 or A-101-WART-302 study. Both WART-301 and WART-302 were double-blind studies where subjects were treated with either active A-101 45% topical solution or vehicle solution. To best account for all potential exposure to A-101 45%, summaries and analyses will take into consideration both the current open-label treatment status as well as the randomized treatment assignment from the subject's respective double-blind study. This classification precipitates the following four treatment groups.

- Open Label A-101 45%: Double-Blind A-101 45%
- Open Label A-101 45%: Double-Blind Vehicle
- Open Label Not Treated: Double-Blind A-101 45%
- Open Label Not Treated: Double-Blind Vehicle

Depending upon analysis population, data will be summarized into all or a subset of treatment groups indicated above. Summaries on All Enrolled Population will display all four treatment groups. Summaries on Safety Population will display only first two treatment groups.

All data listings will be sorted by treatment group and subject ID. Subject ID will identify site number and double-blind study subject participated prior to open label study

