### 3.3 Study Day and Period Study Day

As shown in [Figure 1](#), subjects can potentially take multiple courses of treatment throughout the study. Subjects entering the study with warts will receive treatment at study entry as shown in [Table 2](#). Subjects who enter without any common warts do not receive study medication immediately and follow visit schedules shown in [Table 3](#). If these subjects develop any wart during the study, they will then begin a treatment regimen and follow the visit schedule for treated subjects. Subjects can initiate a treatment regimen up to three times (cycles) throughout the course of the study up to day 122. To allow for comparisons referencing each treatment cycle, Study Day will be calculated in two ways. Study day is defined as the relative day in the study from time of enrollment (first dose if treated immediately). Period study day is defined as the relative day from the day of first dose within a treatment cycle.

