### **3.11.3 Local Skin Reactions**

The number of subjects with local skin reaction signs or symptoms that worsened by at least 1 grade from baseline any time after the first application of study medication will be tabulated by treatment group for each LSR as well any LSR. A separate summary limited to LSRs that worsen and which occur within 30 days of the last application of study medication will be provided. Additionally, to assess effect of number of cycles of applications of study medication on LSR, this summary will be presented by treatment cycle also.

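### The by-cycle LSR table in SAP 3.11.3 cannot show the effect of number of cycles: each column holds a different, selected set of subjects, and cycle number is not cumulative A-101 exposure

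*SAP*

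**What the plan says.** SAP 3.11.3 counts subjects whose LSR signs or symptoms "worsened by at least 1 grade from baseline any time after the first application of study medication will be tabulated by treatment group". It then adds the by-cycle version with its purpose: "to assess effect of number of cycles of applications of study medication on LSR, this summary will be presented by treatment cycle also". It names no common cohort, within-subject comparison or model.

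Treatment group is defined in SAP 3.2, where "summaries and analyses will take into consideration both the current open-label treatment status as well as the randomized treatment assignment" from the parent study. The same section says "Summaries on Safety Population will display only first two treatment groups": open-label A-101 after double-blind A-101, and open-label A-101 after double-blind vehicle.

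Cycles are counted within WART-303. SAP 3.3 says "Subjects can initiate a treatment regimen up to three times (cycles) throughout the course of the study up to day 122". (Footnote 2 to SAP Table 3 gives Day 102 for subjects who are clear at entry. The argument below does not depend on which day applies.)

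On entry to a further cycle, footnote 6 to Protocol Table 2 says "A-101 will only be dispensed to subjects who have not cleared all their warts, or who have developed new warts". Protocol section 6 makes further courses optional. Protocol 7.3 lists "Unacceptable adverse event" and unwillingness to continue among the reasons for removal from therapy.

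Two baselines could apply. SAP 3.4 resets baseline at the start of each cycle for by-cycle analyses. SAP 3.11 fixes the LSR baseline before the first A-101 application in this study.

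**The concern.** Protocol 4.2 justifies the study by the need for safety data when patients require several courses. The by-cycle table is the only LSR analysis in the SAP aimed at that question, and the SAP gives it a causal purpose. Rates that fall across the columns would be read as reassurance about repeat treatment, and rates that rise as accumulating harm. Neither reading is safe if the people in the columns differ in how readily they react.

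The column labels raise a second problem. A reader will take cycle 1, 2, 3 as the number of courses of A-101, but numbering restarts on entry to WART-303 and no parent-study LSR data enter the table.

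**Working it through.** **The plan's own figure.** Protocol 14.1 and SAP 3.13: 400 × 0.5 = 200 subjects previously on active; 200 × (1 − 0.26) = 148 needing A-101 in this study. The figure reproduces. (The 26% is stated for warts and applied to subjects.) I use 148 only as a starting number.

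**Who is in each column.**
- Cycle 1: every treated subject.
- Cycle 2: those with uncleared, recurrent or new warts who remained on therapy, accepted another course and could start in time.
- Cycle 3: those who met the same conditions twice. On the Table 2 schedule, a second course started at the Day 60 visit reaches its own Day 60 on study Day 60 + 59 = 119. That leaves three days before the Day 122 limit, so cycle 3 will be a narrow subset.

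Reaction may influence who continues. Besides Protocol 7.3, the compliance formula in SAP 3.11.1 subtracts warts with a grade 3 LSR from the warts counted as treated, as it does cleared warts.

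**Illustration.** All inputs are assumptions. Half the subjects have a 10% chance of an LSR per cycle and half 70%. The chance of entering the next cycle depends on whether a reaction occurred.

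Cycle 1 rate: 0.5 × 0.10 + 0.5 × 0.70 = 40.0%.

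*(a) Risk unchanged; 50% continue after a reaction, 80% without.*
- Continuation, low-risk: 0.1 × 0.5 + 0.9 × 0.8 = 0.77. High-risk: 0.7 × 0.5 + 0.3 × 0.8 = 0.59.
- Cycle 2: (0.77 × 0.1 + 0.59 × 0.7)/(0.77 + 0.59) = 0.490/1.36 = 36.0%.
- Cycle 3: (0.77² × 0.1 + 0.59² × 0.7)/(0.77² + 0.59²) = 0.303/0.941 = 32.2%.
- Expected numbers from 148: about 101, then 70.

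*(b) Risk unchanged; 80% continue after a reaction, 60% without.*
- Continuation 0.62 and 0.74.
- Cycle 2: (0.062 + 0.518)/1.36 = 42.6%. Cycle 3: 45.3%.

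*(c) As (a), but each subject's odds rise by 1.2 per cycle.*
- The table shows 40.0%, 38.6%, 37.0%. The true rate in the full cohort is 40.0%, 42.7%, 45.4%.

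*(d) Continuation unrelated to reaction, or no difference in risk between subjects.* With unchanged risk the table stays at 40.0%, so there is no bias.

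*(e) Risks 20% and 60%, odds rising by 1.2, continuation as in (a).* The table still rises: 40.0%, 41.9%, 43.7%.

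**Would pairing continuers cure it?** In case (a), the share who react and continue is 0.40 × 0.5 = 0.20, and the share who continue is 0.20 + 0.60 × 0.8 = 0.68. Continuers' cycle 1 rate is 0.20/0.68 = 29.4%, against 36.0% in cycle 2: a false rise of 6.6 points. Non-continuers' cycle 1 rate is 0.20/0.32 = 62.5%. Pairing replaces a false fall with a false rise, whereas splitting cycle 1 by later continuation makes the selection visible.

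**Number of warts.** One to six warts may be treated per course (Protocol 9.1). If each wart independently has a 20% chance of reacting, the subject-level rate is 1 − 0.8^k: 59% with four warts, 36% with two, 20% with one. A change in the number of warts treated moves the rate with no change in tolerance.

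**Cycle against cumulative A-101 course.**

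| WART-303 cycle | Prior A-101 | Prior vehicle |
|---|---|---|
| 1 | course 2 | course 1 |
| 2 | course 3 | course 2 |
| 3 | course 4 | course 3 |

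**The case against.** The strongest reply is that this is a simple count with no test, in a descriptive study. Discontinuation reasons (SAP 3.5), tables of adverse events leading to discontinuation (SAP 3.11.2) and LSR listings (Protocol 14.4) let a reader see attrition. The endpoint counts any one-grade worsening, so a mild reaction qualifies, and nothing says that mild reactors leave. Severe erythema and edema stop only the application in hand (Protocol 10.7). Removal for an adverse event is permitted, not required.

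Much of this stands. It means that the size of the selection effect is unknown and could be small. It does not rescue the stated purpose: the attrition tables are not linked to LSR by cycle, and the SAP itself says that the table is there to assess an effect.

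A reader might go further and infer three things that the documents do not support.
- *That the SAP ignores the parent-study A-101 course.* SAP 3.2 builds parent assignment into treatment group, and 3.11.3 tabulates by treatment group. The by-cycle table is the same summary repeated, so the split most naturally carries over. Only the labelling point remains.
- *That the table is biased towards reassurance.* Cases (b), (d) and (e) show a false rise, no bias, and a true rise that stays visible. The documents give nothing to choose between these patterns.
- *That a paired table of continuers against one common baseline gives the true change.* It does not when continuation depends on the cycle 1 reaction, and warts first treated in a later cycle may have no score before cycle 1.

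**Conclusion.** The concern holds in a limited form. The by-cycle LSR table cannot serve its stated purpose, because entry to later cycles is selective and nothing in SAP 3.11.3 accounts for that. The bias can run either way. In the illustration with unchanged risk, it moves the cycle 3 rate from 40.0% to between 32.2% and 45.3%. That range rests wholly on assumed risks and continuation rates and is not a forecast for this trial. The effect disappears if subjects do not differ in risk or if continuation is unrelated to reaction.

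Two further points need no assumed rates. Cycle number is one behind cumulative A-101 course in the prior-A-101 group. The SAP also gives two LSR baselines without saying which governs this table. A baseline reset at each cycle can hide a reaction that persists from the previous cycle. A first-application baseline may not exist for a wart that appears later.

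This should be changed before the analysis. It does not undermine the safety analysis as a whole.

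**What to change.** In SAP 3.11.3:
1. Call the existing by-cycle table descriptive, drop the wording about assessing an effect, and show the denominator for each cycle.
2. Within each parent-treatment group, add LSR rates for each cycle by number of cycles eventually received, so that cycle 1 rates appear separately for continuers and non-continuers. Give the reasons for not continuing.
3. Label columns by cumulative A-101 course: 2 to 4 in the prior-A-101 group and 1 to 3 in the prior-vehicle group. State that parent-study LSR data are not included.
4. If an effect of number of courses is to be stated, estimate it from all treated subjects with a likelihood-based random-intercept logistic model containing cumulative course number and number of treated warts. Do not take it from a paired table of continuers alone.
5. Reconcile the per-cycle baseline in SAP 3.4 with the first-application baseline in SAP 3.11 for this table. Say how newly treated warts and persisting reactions are handled.

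The cost is SAP wording and one or two extra tables from data already collected, plus the model if item 4 is taken up. Numbers in cycle 3 will be small. The model assumes that continuation depends only on observed data, and the report should say so.

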### **3.11.4 Laboratory Evaluations**

Shift tables showing changes in relationship to the normal reference range grade from baseline to the "worst" relationship recorded post-baseline are tabulated. In the event a subject had both "low" and "high" post-baseline values the subject will be counted under both "low" and "high". As such, the percentages of the cells in the shift table may add to more than 100%.

Chemistry and hematology parameters will be summarized using descriptive statistics for each visit. Both actual values and changes from baseline will be summarized.

The number and percentage of subjects meeting criteria for hepatobiliary abnormalities will be provided.

### **3.12 Interim Analyses**

No interim analyses are planned for this study.

### **3.13 Sample Size**

The sample size is based on an estimate of how many subjects will be required to provide at least 100 subjects requiring repeated treatment for a wart over the course of the study.

- By recruiting 400 subjects, we estimate 200 subjects will have received active treatment in the A101-WART 301/302 studies.
- We expected approximately 26% of warts treated in A-101-WART-301/302 studies to be clear at the end of the A-101-WART-301/302 studies.
- Based on the assumption that 26% of warts will be clear, at least 148 subjects will require exposure to active treatment.
- We anticipate that some subjects originally randomized to vehicle (in double-blind studies) will be exposed to active treatment.

As a result, the study should exceed the target of exposing more than 100 subjects to repeated treatments over the course of the study.

### **3.14 Changes in/ Clarifications to the Conduct of the Study or Planned Analysis**

Originally, both efficacy (primary and secondary endpoints) and safety analyses were planned on intent to treat (ITT) population. The primary objective of the study is to evaluate long-term safety of A-101 45% when applied twice weekly to common warts. Considering this and the fact that all treated subjects will administer the same medication (A-101 45%), it was deemed more appropriate to conduct both efficacy and safety analyses on the Safety Population. For that reason, all analyses will be conducted on the Safety Population. Data collected for subjects who did not receive treatment will be listed.

## **4. STATISTICAL SOFTWARE**

All data summaries and listings will be performed using SAS® Version 9.4 or higher, under Windows operating system.

## APPENDIX A: ASSIGNMENT TO ANALYSIS VISIT

Due to the possibility of deviation from the protocol schedule as well as to incorporate data from unscheduled and/or early termination visits, analysis visits are defined below based on Treatment Period Study Day for each treatment cycle. These analysis visits are based on the nominal, scheduled visits in the protocol and treatment cycle. Analysis visit will be used in analyses performed by or on specific visit as well as for the identifiers on data listings. Both nominal visits as collected on the CRF and analysis visits will be retained in the SAS ADaM datasets.

Analysis Visits Within Each Treatment Cycle:

Analysis Visit	Treatment Period Study Day Range	Target Treatment Period Study Day
Px V1	1	1
Px V2	2 - 22	15
Px V3	23 - 36	29
Px V4	37 - 51	43
Px V5	52 - 81	60
Px V6	82 - 127	102
Px V7	128 - 163	144
EOS (End of Study) Visit	$\geq 164$	182

Note: P indicates Treatment Period (Treatment Cycle), x indicates Treatment Period Number (Either 1 or 2 or 3), and V indicates Visit. There is only one EOS visit for all subjects.

In the event that more than one observation falls into the same study day range, the value closest to the “target day” is selected. If there’s a tie in the absolute distance from the target day, the observation with the greater cycle day is selected.
